2.7.2 Aim 2 Analysis (TA vs TA+CEP)

The main analysis is of client outcomes. Using client/community member baseline and 6-month follow-up, we will evaluate CEP versus TA effects on primary (MHRQL, PHQ-8) and secondary/exploratory outcomes (e.g. mental wellness, homelessness risk factors, behavioral health hospitalizations; physical activity, productivity, self and community efficacy for coping, use of service for depression, social determinants and disaster preparedness and response, others as identified). For secondary analysis of programs, outcomes are training participation and partnerships with other service programs for depression, social determinants and disaster threat/exposure, examining intervention effects controlling for type of service sector for programs, and for community, reporting chi-square statistics. For staff/providers, also considered secondary, main outcomes are participation in training, providing community services and using problem-solving and other strategies for depression, social risk factors and disaster threat/exposure based on data from 12 month follow-up and logs at training events. In two-level hierarchical models, we will compare intervention effects on hours in training using two-part models for skewed distributions.^{10,34}

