2.5 Randomization

2.5.1 Program-level (CEP vs TA)

Within each community, programs will be matched based on a) range of services offered, b) clientele base (i.e. people with serious mental illness, formerly incarcerated people, etc.), c) program size, and d) existing partnerships or affiliations. “Affiliation” refers to having a strong referral relationship and/or clients within and across programs. Programs that match on multiple categories or identify that they are part of an existing partnership or affiliation will be paired. Matched pairs will fall within four different types of grouping:

- 1) Unique Program: There is no similar program to match with. Will be randomized independently.
- 2) Paired Program: Two programs that are similar in the criteria described above are paired and do not have affiliations with other programs in the study. One program is randomly assigned to one of the interventions. The other program will be assigned to the other intervention.

- 3) Unique Cluster: Programs that are affiliated with more than one other program. All programs in the cluster will be treated and randomized as one unit.
- 4) Cluster Pair: Two sets of clustered programs that are reasonably similar as a whole to each other. One cluster will be randomized to one of the interventions. The other cluster will be assigned to the other intervention.

By pairing programs following this schema, we reduce the chance of intervention contamination; that is, an individual client may receive services from multiple programs enrolled in the study. Community Investigators in the C-LEARN Leadership Council will review matching to ensure that programs are appropriately paired.

After matching, we will then randomize programs or program clusters using a random seed to TA or TA+CEP.^{24,27} All interventions are “encouragement” interventions. That is, participants are encouraged to consider interventions to which they are assigned, no one is forced to follow a given protocol. This is more of a public health rather than a clinical approach to intervention implementation.

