2.6.7 Power calculations

The power calculations were based on expecting a percentage point difference between groups ranging from 8 to 10. With enrolling 600 to 720 individuals per group (1200 to 1440 in total), 80% power was projected to detect the difference between groups ranging from 9.3% to 10.7% with alpha level of 0.05 (two-sided) and ICC=.01, allowed a retention rate of 65-75% at 6 months follow-up.²⁷ For outcome measures assessed monthly during the 6-month period, the proposed sample size with 60% retention is adequate for a between group difference of 7.3-7.9%.

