2.7 Proposed Analysis

2.7.1 General Issues

a) Modeling. We will use an intent-to-treat (ITT) framework and hierarchical approach with information on programs, service providers/staff, and clients. We will conduct bivariate analyses to identify potential covariates for multiple regressions and compare unadjusted and adjusted intervention coefficients to assess confounding. We will explore transformations and two-part models for skewed counts with smearing estimates for retransformation. b) Missing data. For missing data (item or survey non-response) we will use logical imputation for items as

appropriate and hot-deck multiple imputation using a predictive mean-matching method for item non-response.^{29,30} c) Weights. We will create enrollment weights to represent intended populations.^{31,32} d) Multiple Comparisons. We will consider methods that incorporate bounds on probability of false findings of significance, e.g., false discovery rate.³³ e) Multilevel Data: We will apply multi-level (i.e., hierarchical or random coefficient) models to account for clients within programs and three-levels for longitudinal data having repeated measures within clients.²⁷

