2.7.3 Aim 3 Analysis: (CR app vs CR+eCBT app)

In regression models above (6-month endpoint or longitudinal), we will include as intervention indicators, CEP vs TA, CR app vs. CR+eCBT app, and their interaction. From estimated models, we will contrast a linear combination of coefficients to estimate CR vs CR+eCBT effects within each CEP or TA group and average effects across these interventions; and conduct stratified analyses by client baseline measures.

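### The primary client models for CEP vs TA do not pre-specify a community term, although programs are matched and randomised within community

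*Combined protocol and SAP*

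**What the plan says.** **Allocation.** Section 2.5.1 begins "Within each community, programs will be matched based on" and lists services, clientele, size and affiliations. Paired programs and paired clusters are split between the arms. Unique programs and unique clusters are randomised on their own. Sections 2.6.1 and 2.6.2 plan two communities, New Orleans and Coastal South Louisiana, with up to 30 programs each and up to 60 in all.

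**Client analysis.** Section 2.7.2 makes client outcomes the main analysis: "Using client/community member baseline and 6-month follow-up, we will evaluate CEP versus TA effects on primary (MHRQL, PHQ-8"). Section 2.7.1(e) gives the clustering: "We will apply multi-level (i.e., hierarchical or random coefficient) models to account for clients within programs", with a third level for repeated measures. Section 2.7.3 gives the named fixed terms: "we will include as intervention indicators, CEP vs TA, CR app vs. CR+eCBT app, and their interaction". Section 2.7.1(a) leaves other covariates to bivariate screening, followed by a comparison of unadjusted and adjusted intervention coefficients. No covariate is named.

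**Program analysis.** For the secondary analysis of programs, section 2.7.2 does name community: "examining intervention effects controlling for type of service sector for programs, and for community, reporting chi-square statistics".

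**Power.** Section 2.6.7 plans for 600 to 720 clients in each arm. On that basis it states that "80% power was projected to detect the difference between groups ranging from 9.3% to 10.7" points. The calculation takes "alpha level of 0.05 (two-sided) and ICC=.01" and assumes that 65-75% of clients are retained at 6 months. It does not say whether the ICC is within or across communities.

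**The concern.** Community is the stratum inside which programs are matched for allocation. The usual rule is to analyse by the groups that the randomisation respects. Here the plan commits to that in a secondary analysis but not in the primary one.

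If the two communities differ on the outcome and the model omits them, the difference is counted as between-program variance. Matching within community has already protected the CEP vs TA estimate from much of that variance, but the model standard error still includes it. The interval is then wider than it need be.

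Screening is not a substitute. Community might be selected for MCS-12 and not for PHQ-8, and the choice would depend on the data. The plan also has little power to spare: section 2.6.7 expects differences of 8 to 10 points, against a detectable difference of 9.3 to 10.7.

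**Working it through.** **Inputs from the documents.** 600 to 720 enrolled per group, 65-75% retained, two-sided alpha 0.05, 80% power, ICC .01 (section 2.6.7); up to 60 programs, 30 per community (section 2.6.2).

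**Assumptions.** 30 programs per arm, proportions near 50% (no base rate is given), equal program sizes, arms balanced within community, and programs treated as independent units.

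**Step 1: the plan's own figure.** Let n be analysed clients per arm, m = n/30 and DEFF = 1 + (m - 1) × ICC. The detectable difference is (1.96 + 0.84) × sqrt(2 × 0.25 × DEFF / n).
- Low end: n = 600 × 0.65 = 390, m = 13, DEFF = 1.12, giving 10.6 points. Power at 10.7 points is 0.808.
- High end: n = 720 × 0.75 = 540, m = 18, DEFF = 1.17, giving 9.2 points. Power at 9.3 points is 0.808.

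The stated 9.3 to 10.7 therefore reproduces, with no community term in the calculation.

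**Step 2: ICC .01 already includes community variance.** At the extreme, a community term removes all of it and DEFF falls to 1.
- m = 13: standard error ratio sqrt(1/1.12) = 0.945, a 5.5% reduction; detectable difference 10.6 to 10.0 points.
- m = 18: sqrt(1/1.17) = 0.925, a 7.6% reduction; 9.2 to 8.5 points.

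If the term removes half, the detectable differences are 10.3 and 8.9 points. The planned 80% is reached without the term, so what is forgone is extra precision.

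**Step 3: ICC .01 is within community.** If two equal communities differ by D, omitting the term adds (D/2)² / 0.25 to the ICC: .0025, .01 or .0225 for D = 5, 10 or 15 points. The inflation is sqrt(DEFF without the term / DEFF with it). The estimate's true spread does not change when arms are balanced; only the model standard error grows. Power at the planned detectable difference is therefore Φ(2.80 - 1.96 × inflation), and two-sided type I error is 2 × (1 - Φ(1.96 × inflation)).

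| D (points) | m | DEFF without / with | SE inflation | Power | Type I error |
|---|---|---|---|---|---|
| 5 | 13 | 1.15 / 1.12 | 1.3% | 79% | 4.7% |
| 5 | 18 | 1.2125 / 1.17 | 1.8% | 79% | 4.6% |
| 10 | 13 | 1.24 / 1.12 | 5.2% | 77% | 3.9% |
| 10 | 18 | 1.34 / 1.17 | 7.0% | 76% | 3.6% |
| 15 | 13 | 1.39 / 1.12 | 11.4% | 73% | 2.9% |
| 15 | 18 | 1.5525 / 1.17 | 15.2% | 71% | 2.4% |

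**Step 4: simulation.** Program means were simulated for 60 programs, 30 per community, 15 per arm in each, with 20,000 trials. With m = 13 and communities 0.2 SD apart (10 points at 50%), the model without community had a mean standard error of 0.080 against a true 0.076, and a type I error of 3.6%. With the term these were 0.0755 and 4.7%. With m = 18 the figures without the term were 0.0706 against 0.066, and 3.5%; with it, 0.0655 and 5.1%.

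**Step 5: chance imbalance.** Suppose one community splits 18 CEP / 12 TA and the other 12 / 18. The first community then supplies 60% of CEP programs and 40% of TA programs. A 10-point community difference moves the unadjusted estimate by (0.60 - 0.40) × 10 = 2 points. The split is illustrative; the documents give none.

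**The case against.** **Silence is not exclusion.** A reader might infer that the plan rules community out of the client models. It does not. Section 2.7.3 lists intervention indicators, not a full covariate list, and section 2.7.1(a) leaves room for community through screening. A large community difference is also one that screening would probably find. This stands: the gap is in pre-specification.

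**Imbalance is not bias.** A reader might also infer that the CEP estimate is confounded by community. Any uneven split from independently randomised units is chance under randomisation, and section 2.7.1(a) plans an adjusted comparison. This stands too. The 2-point shift above shows what one unlucky allocation could leave in an estimate; it is not a systematic error.

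**The larger losses need an unsupported number.** Differences of 10 or 15 points imply a total ICC of about .020 or .032, two to three times the planned .01. If .01 is the total, which is a natural reading of an unqualified ICC, planned power is intact. This stands, and it is why both readings are shown.

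**Baseline may absorb the difference.** Section 2.7.2 uses baseline as well as 6-month data. Assume a baseline to follow-up correlation of 0.5 (not in the documents), a community difference already present at baseline, and an ICC still .01. Then 0.2 or 0.3 SD becomes 0.2 × 0.5 / sqrt(0.75) = 0.115 or 0.3 × 0.5 / sqrt(0.75) = 0.17 residual SD. The formula of step 3 then gives inflation of about 2% or 4-5%, and power of about 79% or 77-78%. The plan does not state its baseline adjustment, so this is a possibility only.

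**There may be one community.** The Part 3 protocol describes the trial as centred on Orleans Parish, and the program numbers in section 2.6.2 are ceilings. With one community the term has no effect. That makes it harmless, but Parts 1 and 2 still plan two.

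**Apps are randomised by client.** The CR vs CR+eCBT contrast is mainly within program and gains little from a community term. This stands.

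None of these points commits the primary model to the allocation stratum.

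**Conclusion.** The point holds as a gap in pre-specification. The plan uses community in allocation and in the secondary program analysis, but leaves its place in the primary CEP vs TA client models to data-driven screening.

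The size is uncertain because no between-community difference is given. It runs from no loss of planned power, with up to about 5-8% of the standard error forgone (ICC .01 covers community), to a standard error 11-15% too large and power of 71-73% (ICC .01 within community, 15-point difference, no baseline adjustment). The middle case, a 10-point difference, gives 5-7% and 76-77%.

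The direction is conservative. With arms balanced within community, type I error falls below 5%, so the documents do not support a reading that false positives are inflated. Nor do they support a firm statement that the trial is underpowered for this reason. The range rests on 60 programs treated as independent and equal in size; pairing and clustering would change the exact figures.

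**What to change.** State in sections 2.7.1(e) and 2.7.2 that the client and staff/provider models for CEP vs TA include a fixed effect for community, set in advance and exempt from bivariate screening, and that the term drops out if only one community is enrolled. Carry the same term in the combined model of section 2.7.3 for consistency, with little gain expected for the app contrast. In section 2.6.7, say whether ICC .01 is within or across communities.

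The cost is a sentence or two of analysis wording and one degree of freedom. No new data are needed, since community is known for every program.

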2.4.2 Administrator/Provider Measures

Administrator measures for baseline and 6 months include organization partnerships for depression, social risk factors and disaster services. We will also assess program size, services offered, aspects of organizational structure, and at follow-up, participation in planning and trainings.^{8,24,25} Provider or staff measures include time spent providing community services and intervention-relevant practices (e.g., problem-solving, screenings for depression, social risk factors, and disaster preparedness) (primary), and self and community efficacy to address stressors and disasters, and at baseline, training and job status.^{8,10,26} These measures have received Leadership Council and community stakeholder input.

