2.6.2 Programs

We will select eligible programs by combining program lists with community nominations, classifying programs as mental health, substance abuse, primary care/FQHCs/public health (health) or social services, community centers, parks and recreation community centers, businesses, salons, gyms, faith-based, and disaster preparedness/response programs (community).²⁸ We will invite programs through letters, phone calls and visits to recruit as many as 30 per community, expecting as many as 60 total programs.

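### The program-level partnership analysis names sector and community as controls but leaves the program's own baseline partnership measure, which is already collected, to data-driven covariate screening

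*Combined protocol and SAP*

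**What the plan says.** Section 2.7.2 treats programs as a secondary analysis in which "outcomes are training participation and partnerships with other service programs for depression, social determinants and disaster threat/exposure". It describes that analysis as "examining intervention effects controlling for type of service sector for programs, and for community, reporting chi-square statistics". The baseline and 6-month wording at the start of 2.7.2 concerns client outcomes, not program outcomes.

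The baseline value exists. Section 2.4.2 says: "Administrator measures for baseline and 6 months include organization partnerships for depression, social risk factors and disaster services".

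Section 2.7.1(a) adds a general rule: "We will conduct bivariate analyses to identify potential covariates for multiple regressions and compare unadjusted and adjusted intervention coefficients to assess confounding". It does not mention the baseline value of the outcome.

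On the number of units, section 2.6.2 is "expecting as many as 60 total programs". Section 2.5.1 lists "c) program size, and d) existing partnerships or affiliations" among the matching criteria, and says of affiliated programs: "All programs in the cluster will be treated and randomized as one unit".

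**The concern.** The number of partners a program has at 6 months is likely to depend on how many it had at the start. If so, a model without the starting value carries avoidable between-program variance. Clients number 1200 to 1440 in the power section, but programs number at most 60, so precision is scarcer at program level. The plan gives no power figure for this analysis. Building relationships across sectors is one of the end-goals of CEP in 2.3.2, so the outcome has some interpretive weight although it is secondary.

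There is also a question of pre-specification. Two analysts following the text could report different models for the same outcome, depending on how each applied the screen.

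**Working it through.** **The plan's own figure.** The only power statement (2.6.7) is at client level: detectable differences of 9.3% to 10.7%. It reproduces closely if one assumes 30 programs per arm and rates centred on 50%.
- 600 × 0.65 = 390 retained; 390/30 = 13 per program; design effect 1 + 12 × 0.01 = 1.12; effective n = 390/1.12 = 348; detectable difference 10.6%.
- 720 × 0.75 = 540 retained; 540/30 = 18 per program; design effect 1 + 17 × 0.01 = 1.17; effective n = 540/1.17 = 462; detectable difference 9.2%.

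This says nothing about the partnership analysis, which has no stated figure to reproduce.

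**Inputs for the program level.** From the documents: at most 60 programs (2.6.2), and two-sided alpha 0.05 (borrowed from 2.6.7). Assumed: 30 independent units per arm, a continuous partnership score, and r, the correlation between baseline and 6-month partnerships that remains after sector and community. The range taken is 0.3 to 0.7. Effects are in units of the residual SD after sector and community. The few degrees of freedom those two terms use are ignored.

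**Formulas.** Without the baseline value, power comes from the noncentral t with 58 degrees of freedom and noncentrality d × √(30/2). Power is 80% at d = 0.736. With the baseline value, the residual SD is multiplied by √(1 − r²), so d becomes d/√(1 − r²), with 57 degrees of freedom. The number of unadjusted programs giving the same precision is 60/(1 − r²).

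| r | Variance cut (r²) | √(1 − r²) | Power at d = 0.736 | d detectable at 80% | Equivalent programs |
|---|---|---|---|---|---|
| 0 (not adjusted) | 0 | 1 | 80% | 0.736 | 60 |
| 0.3 | 9% | 0.954 | 83.5% | 0.702 | 66 |
| 0.375 | 14% | 0.927 | 85.6% | 0.682 | 70 |
| 0.5 | 25% | 0.866 | 89.9% | 0.637 | 80 |
| 0.7 | 49% | 0.714 | 97.5% | 0.525 | 118 |

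**Why r must be the remaining correlation.** Sector and community are already in the model. Suppose the raw correlation is 0.5 and those two factors explain 20% of the variance at each time, acting in the same direction (an assumption). The remaining correlation is (0.5 − 0.2)/√(0.8 × 0.8) = 0.3/0.8 = 0.375, which is the third row. Reading the 0.5 row off a raw correlation of 0.5 would overstate the gain.

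**Fewer units.** With 20 or 15 independent units per arm, the power gain from an 80% starting point agrees with the table to within about 0.1 point. The absolute precision is of course worse.

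**Validity.** In simulations with 30 per arm, 4,000 runs per setting and no true effect, rejection was 4.6% to 5.1% without the baseline value and 4.7% to 5.2% with it, for r from 0 to 0.7.

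**The case against.** The strongest objection is that 2.7.2 does not say its two controls are the only ones, and that 2.7.1 applies to program data too. The plan states no screening threshold. If it were p < 0.05 with 60 programs, the Fisher z approximation gives the chance of selecting baseline partnerships as Φ(atanh(r) × √57 − 1.96): about 65% at r = 0.3, 89% at 0.4 and 99% at 0.5. So where adjustment helps most, the screen would probably bring the covariate in. That stands, and it narrows the point. What remains is that entry depends on the data and on an unstated rule, and that the stated purpose of comparing coefficients is to assess confounding, not to gain precision.

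A reader might infer that omitting the baseline value biases the result. The documents do not support that. Under randomization, baseline differences between arms are chance differences, and the unadjusted standard error already includes them, as the rejection rates show. Counting such imbalance as well as the power loss would count the same variance twice.

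A reader might also infer that the plan matches on this very measure and then ignores it. That is not established. In 2.5.1, affiliation means referral ties or shared clients, and pairing is justified as limiting contamination. Nothing shows that it is the quantity in the administrator survey.

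Two further points stand. Section 2.7.2 does not say whether the outcome is a 6-month level, a change or new partnerships, and the last two would already use baseline. And the outcome is secondary: the program-level hypotheses in 2.1 concern training and service use, not partnerships.

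**Conclusion.** The point holds as one of precision and pre-specification. The plan names sector and community for the partnership outcome, does not name a baseline measure it already collects, and leaves its use to a data-driven screen. The comparison is valid without it.

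The loss is small at a remaining correlation of 0.3 (about 3.5 points of power) and material at 0.5 or more (about 10 points or more). All of this rests on an assumed correlation, a continuous 6-month score and 30 independent units per arm. Sixty programs is a ceiling, and clusters randomized as one unit reduce the number of independent units further. The main client-level analysis is unaffected.

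**What to change.** In 2.7.2, for partnership outcomes measured at 6 months, state the controls as: *type of service sector, community and the program's baseline value of the same partnership measure*. Say that standard errors will respect the randomized unit (program, matched pair or cluster). Without that, adding a covariate to a model that treats affiliated programs as independent could make the standard errors too small. Report the adjusted difference with its confidence interval alongside the chi-square statistic. Training participation has no baseline value and stays as planned.

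The cost is one degree of freedom and a short text change; the data are already due to be collected. One item needs a decision. The hot-deck imputation in 2.7.1(b) is named for item non-response and does not clearly cover a baseline administrator survey that is missing altogether, so the text should say how such programs are handled.
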